mechanisms of insulin resistance, and the development of a non-invasive biomarker in children at an increased risk of developing insulin resistance.

Hypothesis and Specific Aims

We hypothesize that when compared to normal weight or obese insulin sensitive children, obese insulin resistant children will exhibit altered circulating blood cell bioenergetics and a more oxidized plasma redox state and that these alterations will be associated with decreased resting energy expenditure and impaired fatty acid oxidation (FAO). Furthermore, we hypothesize that poor oxidative capacity over time may distinguish between metabolically healthy obese (MHO) and metabolically unhealthy obese (MUO) phenotypes, as well as be predictive of T2D development. We also hypothesize that bioenergetics, REE and FAO will be improved in obese T2D or insulin resistant children after 6 months of metformin therapy that will be prescribed as part of their clinical care. To test these hypotheses, we will evaluate the following Specific Aims:

Specific Aim 1: Determine whether peripheral blood mononuclear cell (PBMC) and platelet bioenergetics (oxidative phosphorylation, glycolysis and fatty acid oxidation) are impaired and whether plasma glutathione-mediated redox/antioxidant capacity is decreased in obese insulin resistant children as compared to normal weight and obese insulin sensitive children.

Specific Aim 2: Determine whether resting energy expenditure (REE) and fatty acid oxidation (FAO) are decreased in obese insulin resistant as compared to lean and obese insulin sensitive children and whether REE and FAO are correlated with bioenergetic and redox profiles.

Specific Aim 3: Determine whether the bioenergetic oxidative capacity measured in circulating cells, PBMCs/platelets, and FAO are valuable predictive markers of T2D in obese children, in addition to distinguishing MUO from MHO subjects.

Specific Aim 4: Determine whether circulating blood cell bioenergetics and whole-body REE and FAO are modulated by metformin therapy that will be prescribed as part of clinical care in

Title: Bioenergetics and Metabolism in Pediatric Populations

PI: [name].

obese children with T2D or insulin resistance.

Study Design and Procedures

This study consists of:

1. An observational cross sectional bioenergetic and metabolic analysis of several groups of children including lean, obese, and T2D.

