- Participants in the obese-insulin resistant group may be asked to complete one additional study visits to occur at 12 months (\pm 2 weeks) after the initial study visit. This is to follow changes in bioenergetic and metabolic parameters over time to assess validity and will help establish not only the degree of change in the studied outcomes, but also their predictive value for T2D development, in addition to distinguish between metabolically healthy obese (MHO) and metabolically unhealthy obese (MUO) phenotypes. We may request that all obese insulin resistant participants complete one additional study visit; however, this additional study visit is optional as we do not want to discourage potential enrollment due to the possibility of another visit or lengthy visit. We anticipate roughly 43% of the 70 obese insulin resistant participants will decline a 2nd study visit with a goal of 40 subjects completing a second visit at 12 months (\pm 2 weeks).
- Participants in the newly prescribed metformin group who are prescribed metformin as part of their clinical care will be asked to complete a second study visit to occur six months (\pm 2 weeks) after beginning metformin therapy prescribed as part of their clinical care. We may request that all 20 participants in this group complete the additional study visit; however, the additional study visit is optional as we do not want to discourage potential enrollment due to the possibility of multiple visits or lengthy visits. We anticipate 50% of the 20 participants in this group will decline a 2nd study visit with a goal of 10 subjects completing a 2nd visit at 6 months (\pm 2 weeks).

A participant/parent pair will be compensated \$100.00 in gift cards for each study visit completed. Completion of the study visit may include participation in parental study forms, anthropometric

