measurements, fat oxidation estimate measured by deuterated palmitate, blood sample, urine samples, body composition assessment, and resting energy expenditure by indirect expenditure. Because the parent and participant do not have to stay at the study location for the entire visit, completion of the study visit would occur once the samples are obtained by the research personnel. Parents/participants who are healthy with a normal weight and also healthy obese children, will be given a one-time \$100.00 in gift cards for participation in the research study visit. Parents/participants with T2D or insulin resistance who are prescribed metformin therapy at their normally scheduled doctor visit or part of the obese with insulin resistance group will be asked to complete two study visits and will be paid up to \$200.00 in gift cards (\$100.00 in gift cards at the first study visit and \$100.00 in gift cards at the second visit). For each study visit, a \$50 gift card will be provided to the study participants/parents after completion of the procedures to be completed at the research site (e.g., anthropometric measurements, Tanner Stage Assessment, physical activity questionnaire, depression scale, and blood collection) and another \$50 gift card will be given to the study participants/parents upon return of the study samples and intake of food and liquid form from the visit. Those participants/parents who are asked to return to re-attempt procedure(s) not successfully completed at a study visit (initial or second) will be given a \$25 gift card after re-attempting to complete the procedure(s). Participants/parents may be given up to \$20 in ACRI merchandise. Breakfast, lunch and snacks may be provided during study visits.

Study Population

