- Age 5-9 years and Tanner stage as reported by parent no greater than stage 1 OR Age 5 years - 17 years 5 months, diagnosed with type 2 diabetes mellitus or insulin resistance and prescribed metformin (not yet taking)
- Either healthy lean ($BMI \geq 5^{\text{th}}$ percentile and $< 85^{\text{th}}$ percentile for age/sex) or obese ($BMI \geq 95^{\text{th}}$ percentile for age/sex)
- For those with $BMI \geq 95^{\text{th}}$ percentile for age/sex, parental verbal confirmation will be obtained that the child had a history of $BMI \geq 95^{\text{th}}$ percentile for age/sex for at least six months prior to study enrollment

Exclusion criteria:

- Genetic or physical conditions impacting mobility over past year as determined by the PI
- Having known chronic illnesses/disorders that may independently affect study outcome measures: type 1 diabetes mellitus, neurologic (e.g. epilepsy), developmental (developmental delay, autism spectrum disorder), endocrine (thyroid, Cushing's), hepatic, autoimmune, cardiac and renal disorders. Also, chronic lung disorders except well controlled asthma that does not require permanent use of inhaled/oral steroids
- Taking any of the following medications that can affect study outcome: antipsychotics, thyroid hormone replacement therapy, inhaled/oral steroids, insulin, anabolic drugs (growth hormone replacement therapy and oxandrolone) and stimulants
- Taking metformin prescribed as part of their clinical care at the time of enrollment (may begin metformin therapy prescribed as part of their clinical care while enrolled in the study)
- $BMI < 5^{\text{th}}$ percentile for age/sex (classified as underweight based on CDC growth charts)
- Subjects determined ineligible by the PI.

Risks and Benefits

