For Aim 3: A paired t-test will be used to compare the mean change in the various outcomes described in SA1 and SA2 from baseline to 12 months for pre-pubertal insulin resistant obese children. If the assumptions for the paired t-test are not met, the non-parametric Wilcoxon matched-pairs signed-ranks test will be used. Alternatively, generalized linear mixed models (GLMM) will be used for Aim 3. GLMM account for the dependence between measurements from the same individual taken over time and allow the inclusion of fixed and time varying covariates.

For Aim 4: A paired t-test will be used to compare the effects of metformin on the various outcomes on obese T2D/insulin resistant children with a new metformin prescription. If the assumptions for the paired t-test are not met, the non-parametric Wilcoxon matched-pairs signed-ranks test will be used. Alternatively, generalized linear mixed models (GLMM) will be used for Aim 4. GLMM account for the dependence between measurements from the same individual taken over time and allow the inclusion of fixed and time varying covariates.

Sample Size Justification:

For Aims 1 and 2, statistical power was computed based on a one-factor ANOVA with a total of 110 children (70 obese insulin resistant, 20 healthy obese, 20 healthy lean). Assuming 80% power and $\alpha = 0.05$, the minimum detectable Cohen's f effect size (ES(f)) is 0.33. This is a medium effect size and should provide valuable information regarding whether a large study is warranted.

For Aim 3, statistical power was computed based on a paired t-test with a total of 40 children. Assuming 80% power and $\alpha = 0.05$, the minimum detectable Cohen's d effect size (ES(d)) is 0.45 for those who completed the study. These are medium effect sizes and should provide valuable information regarding whether a large study is warranted.

For Aim 4, statistical power was computed based on a paired t-test with a total of 10 children. Assuming 80% power and $\alpha = 0.05$, the minimum detectable Cohen's d effect size (ES(d)) is 1.0. Although this effect size is large, it should provide valuable information regarding whether a large study is warranted.

Ethical Considerations

This study will be conducted in accordance with all applicable government regulations and University of Arkansas for Medical Sciences research policies and procedures. This

Title: Bioenergetics and Metabolism in Pediatric Populations

PI: [name].

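### Aim 4 words a one-group change to six months on metformin as an effect of the drug; secondarily, Aim 3 does not say how children who start metformin or leave Tanner 1 are handled

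*Combined protocol and SAP*

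**What the plan says.** **Aim 4.** Under Data Analysis: "A paired t-test will be used to compare the effects of metformin on the various outcomes". Specific Aim 4 asks whether circulating blood cell bioenergetics and "whole-body REE and FAO are modulated by metformin therapy". In the Sample Size Justification, "statistical power was computed based on a paired t-test with a total of 10 children", with 80% power, alpha 0.05 and a detectable d of 1.0. The same paragraph says the result should help decide on a larger study.

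**Who is seen, and when.**
- Lean and healthy obese children have one visit. The compensation text reads "Parents/participants who are healthy with a normal weight and also healthy obese children, will be given a one-time" payment.
- Children in the obese insulin resistant group "may be asked to complete one additional study visits to occur at 12 months".
- The metformin group returns at six months, give or take two weeks, "after beginning metformin therapy prescribed as part of their clinical care".

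**Entry.** The metformin route takes children aged 5 years to 17 years 5 months who are "diagnosed with type 2 diabetes mellitus or insulin resistance and prescribed metformin (not yet taking"). The limit "Tanner stage as reported by parent no greater than stage 1" belongs to the other route, ages 5 to 9.

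**Aim 3.** A paired t-test compares baseline with 12 months in insulin resistant obese children described as pre-pubertal. A signed-rank test is the fallback. A mixed model is offered as an alternative, with no covariate named. The exclusion criteria allow a child to begin metformin after enrolling. Study Design and Procedures lets staff reschedule or cancel a visit when a medication or new diagnosis may make the child ineligible for it.

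**The concern.** Aim 4 attributes to metformin whatever happens between two visits in children who all receive it. Nothing in the design shows what would have happened over the same months without the drug. The protocol's own Tanner item warns that insulin rises sharply in early puberty and that this can mislead the conclusions, yet the metformin group has no Tanner limit. Because the Aim 4 result feeds the decision on a larger study, drift could be taken for a drug effect, or could hide one.

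The measured interval is also loosely defined. Baseline falls before metformin starts, the second visit is timed from the start, and no limit is set on the gap between baseline and start.

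For Aim 3, Tanner 1 is required only at entry and metformin may begin during follow-up. The plan does not say whether the 12-month change describes all children who return or only those still pre-pubertal and untreated.

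**Working it through.** **1. Reproduce the plan's figures.** For a two-sided paired t-test at 0.05, power = P(T > c) + P(T < −c), where T is noncentral t with n − 1 degrees of freedom and noncentrality d√n, and c is the 0.975 quantile of central t. The plan does not state sidedness; two-sided reproduces it.
- n = 10: c = 2.262. Power is 80% at d = 0.996 (noncentrality 0.996 × 3.162 = 3.15) and 80.3% at d = 1.0.
- n = 40: power is 80% at d = 0.454 and 79.3% at d = 0.45.

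Both stated values stand.

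**2. What the Aim 4 test estimates.** Write the mean change as δ + τ, where δ is the drug effect and τ is the change that would have occurred without the drug. The test addresses δ + τ = 0. In this group every baseline is off drug and every follow-up is on drug, so a drug indicator and a visit indicator are the same column. A mixed model on these children cannot estimate δ and τ separately. It could include Tanner stage, but elapsed time would still coincide with treatment. The other groups do not supply τ: two have a single visit and the third returns at 12 months.

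**3. Illustration for n = 10.** The documents give no drift, so these values of τ are assumptions, in SD of change.

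| Drift τ | Significant if δ = 0 | Power if δ = 0.996 and drift opposes it |
|---|---|---|
| 0 | 5% | 80% |
| 0.2 | 9% | 61% (net 0.796) |
| 0.5 | 29% | 29% (net 0.496) |
| 0.8 | 62% | 9% (net 0.196) |

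The 95% interval for mean change is ±2.262/√10 = ±0.72 SD.

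**4. Interval.** If metformin starts 1 or 3 months after baseline (assumed), the off-drug share of the measured interval is 1/7 = 14% or 3/9 = 33%.

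**5. Aim 3.** Suppose 10% to 30% of the 40 returners start metformin or leave Tanner 1 (assumed). That is 4 to 12 children, leaving 36 to 28. By the formula in step 1, a paired test in those remaining detects 0.48 to 0.55 SD, against 0.454 for all 40.

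A mixed model with separate metformin and Tanner terms was checked by generalized least squares, with 70 baselines, 40 follow-ups and within-child correlation 0.3 to 0.7 (assumed). With 4 to 12 affected children split evenly between the two terms, each term has a standard error of about 0.67 down to 0.36 SD of change. If 4 children split 1 and 3, the one-child term has a standard error of about 0.9. For scale, a plain difference in mean change between 2 affected and 36 unaffected children has standard error √(1/2 + 1/36) = 0.73, so the model gains only a little.

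**The case against.** The study calls itself observational, metformin comes from routine care, and the hypothesis is temporal: improvement after six months of therapy. The results are meant to guide later work. The mixed model allows time-varying covariates, and staff may cancel a visit over medication. Every drift and share used above is assumed.

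Much of this stands. It makes the Aim 4 fault one of wording and conclusion, not of test choice, and the illustrations show direction and scale only. It does not rescue the effect wording: a pilot that informs a larger study still has to say what it measured, and no covariate restores the missing untreated change.

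Three stronger readings are tempting, and the documents do not support them.
- **That the Aim 4 sample size is wrong.** It reproduces.
- **That Aim 4 must have a comparator, or that the insulin resistant group could serve as one.** A description of change needs none. That group differs in interval, age and Tanner range, its members may start metformin, and no contrast of change with it is planned.
- **That Aim 3 is invalid, or that a child who turns 10 or starts metformin breaches the protocol.** Ages 5 to 9 are an entry range, and starting metformin is allowed. What is missing is a statement of how such children are analysed. The power to cancel visits is discretionary, does not mention Tanner stage, and is not an analysis rule.

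**Conclusion.** Aim 4 is wrong as worded. Its test, and the d of 1.0, concern mean change from a pre-metformin visit to six months after starting, and the design cannot attribute that change to the drug. This rests on the visit schedule and not on any assumed number. How far the conclusion could mislead depends on drift that the documents do not give; at 0.2 to 0.8 SD the chance of a significant result with an inactive drug would be 9% to 62%.

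Aim 3 is a lesser specification gap. Its paired test and its d are sound for change in the children who return, but the population label and the handling of metformin start and pubertal change need stating. Whether returners represent all such children under usual care also depends on how the cancellation provision is applied.

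**What to change.** **Aim 4.**
- In Specific Aim 4, the Data Analysis paragraph and the sample-size paragraph, describe the quantity, the d of 1.0 and the conclusion as change from the pre-metformin baseline visit to six months after starting metformin, with no effect wording.
- Report the gap from baseline to metformin start, and Tanner stage at both visits.

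The test, visits and sample size do not change. The cost is the causal claim.

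**Aim 3 (secondary).**
- Describe the children as pre-pubertal at entry, and keep the paired t-test in all returners as primary.
- Report how many started metformin or left Tanner 1. This needs the metformin start date recorded for the insulin resistant group; the compliance check is specified only for the metformin group.
- Add a sensitivity analysis limited to returners still at Tanner 1 and not on metformin. It is less precise and selects on status after baseline, so it may drop the children who progressed.
- Reconcile the passage allowing visits to be cancelled for medication or a new diagnosis with the one allowing metformin to begin during the study, and report any visit cancelled on that ground.
- Treat any mixed model with separate metformin and Tanner terms as descriptive only. Besides the large standard errors, the Tanner item itself says the parent form is subjective and can be wrong, especially for obese children, and physician examination depends on parental agreement.

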At the time of collection, samples will be kept on ice or refrigerated (with the exception of stool which will be kept in a freezer) in the pediatric clinical research unit or in [name] laboratory (Rm 4015 of ACRI) until they can be transported to the research laboratory. Samples will be kept at -80°C once the initial processing and analyses have taken place. Samples will be stored in Room N2002 Freezer N2002FT6 or N2002FT18 of ACRI in [name] laboratory. These are monitored continuously for proper temperature and working condition. None of a subject's personal identifiers will be present on any biological sample, except the unique subject ID and the study acronym. The samples may be used until they are used up for research on pediatric nutrition.

At any time if the subject decides that he/she does not want to participate anymore, that subject's data will be included as part of the planned analysis of study data. No more information will be collected after withdrawal, however all data and samples collected prior to withdrawal will still be used.

Information pertaining to this study will be made publically available through the ClinicalTrials.gov website.

Data Analysis

Statistical and Power Analyses: 175 pre-pubertal children ages 5-9 years old will be recruited for this study assuming that 130 subjects stratified across the following groups will complete the study: i) healthy lean (n=20); ii) healthy obese (n=20); iii) obese insulin resistant (n=70); obese

Title: Bioenergetics and Metabolism in Pediatric Populations

PI: [name].

with new metformin prescription (n=20). A one-factor analysis of variance (ANOVA) will be used to compare mean outcome of interest across the groups of children (healthy lean, healthy obese, obese insulin resistant and obese T2D). Pair-wise comparisons using Tukey-Kramer post-hoc tests will be used to identify groups whose means differ significantly while retaining the family-wise error rate at 5%. Outcomes will be also checked to verify that the assumptions of the parametric tests are met. When substantial deviation from assumptions are encountered, and if suitable transformation are not found, groups will be compared using the nonparametric Kruskal-Wallis rank test, followed by Bonferroni corrected Wilcoxon rank-sum tests to identify groups that differ. Generalized linear model (GLM) will also be used to incorporate important covariates and effect modifiers into the analysis.

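### The minimum detectable f of 0.33 for Aims 1 and 2 does not follow from its stated inputs, which give 0.30, and no sensitivity is given for the two pairwise contrasts the aims name

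*Combined protocol and SAP*

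**What the plan says.** The Sample Size Justification bases power for Aims 1 and 2 on "a one-factor ANOVA with a total of 110 children (70 obese insulin resistant, 20 healthy obese, 20 healthy lean"), with 80% power and alpha 0.05. Its result is "the minimum detectable Cohen's f effect size (ES(f)) is 0.33. This is a medium effect size", which it says should help show whether a large study is warranted. It gives no standard deviation, pattern of group means, weighting convention for f, or software.

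The aims themselves are pairwise. Under Hypothesis and Specific Aims, Aim 1 asks about impairment "in obese insulin resistant children as compared to normal weight and obese insulin sensitive children". Aim 2 asks whether resting energy expenditure and fatty acid oxidation "are decreased in obese insulin resistant as compared to lean and obese insulin sensitive children".

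Statistical and Power Analyses plans an ANOVA to "compare mean outcome of interest across the groups of children (healthy lean, healthy obese, obese insulin resistant and obese T2D"), so four groups rather than the three used for power. It then says that "Pair-wise comparisons using Tukey-Kramer post-hoc tests will be used to identify groups whose means differ significantly", with the family-wise error rate held at 5%.

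**The concern.** There are two separate points.

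1. **Arithmetic.** Every input needed for the omnibus calculation is stated, yet the stated f does not come out of it.
2. **Missing sensitivity.** The omnibus f measures how well the F test detects any departure from equal means. It does not say how large a difference between insulin resistant children and either comparator group of 20 can be detected after Tukey-Kramer adjustment, and those two differences are what Aims 1 and 2 ask about. The section claims no pairwise power, so this is an omission and not a second arithmetic error.

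At stake is how the results will be read. Someone told that the study detects a medium effect could take a non-significant difference between insulin resistant and healthy obese children as evidence against a larger study, when the design was unlikely to detect a moderate difference there.

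**Working it through.** **Inputs.** N = 110 in groups of 70, 20 and 20; k = 3; alpha 0.05; power 80% (all from the Sample Size Justification). Tukey-Kramer at a 5% family-wise rate, four groups, and 130 completers (from Statistical and Power Analyses).

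**Attempt to reproduce 0.33.** With f weighted by group size, the F statistic is noncentral F with k − 1 = 2 and N − k = 107 degrees of freedom and noncentrality λ = N·f².

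- 80% power needs λ = 9.91, so f = √(9.91/110) = 0.300.
- At f = 0.33, λ = 110 × 0.33² = 11.98 and power is 87.3%. Simulation agrees (87.3%).
- At 80% power, f = 0.33 needs only about 92 children.

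Other readings of the inputs:

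| Reading | Minimum detectable f |
|---|---|
| 3 groups, N = 110 (as stated) | 0.300 |
| 4 groups, N = 110 | 0.321 |
| 4 groups, N = 130 | 0.294 |
| 3 groups, N = 90 (not stated) | 0.333 |
| 3 groups, N = 110, alpha 0.025 (not stated) | 0.329 |

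The same section's figures for Aim 3 (0.454, stated as 0.45) and Aim 4 (0.996, stated as 1.0) do reproduce.

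**Unweighted f.** If f is the plain SD of the three group means divided by the within-group SD, its minimum detectable value depends on the pattern of means. It runs from 0.294 (the two comparators equal) to 0.406. It equals 0.33 when one comparator mean lies about 67% of the way from the other comparator to the insulin resistant mean. The differences from insulin resistant are then 0.793 and 0.262 SD, and the smaller has 9% Tukey-Kramer power (6% with the four-group critical value).

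**Pairwise sensitivity.** Power comes from the noncentral t with noncentrality d/√(1/n₁ + 1/n₂) and the Tukey critical value: 2.377 for three groups (107 df) or 2.604 for four (130 − 4 = 126 df). For 70 vs 20 the divisor is √(1/70 + 1/20) = 0.2535; for 20 vs 20 it is √(1/20 + 1/20) = 0.3162.

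| Contrast | d for 80% power, 3 groups | d for 80% power, 4 groups |
|---|---|---|
| Insulin resistant vs either comparator (70 vs 20) | 0.82 SD | 0.875 SD |
| Healthy obese vs lean (20 vs 20) | 1.02 SD | 1.09 SD |

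**What f = 0.33 implies for the two aim contrasts.** At a fixed size-weighted f, the smaller of the two differences is largest when the comparator means are equal. Then f² = (70 × 40/110²)·d², so d = 0.33/√0.2314 = 0.686 SD. This caps the power of the weaker contrast whatever the pattern of means. The four-group column applies that critical value to differences derived from a three-group f, so it is a sensitivity case.

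| Case | Difference | Power, 3 groups | Power, 4 groups |
|---|---|---|---|
| Upper bound for the weaker contrast, f = 0.33 | 0.686 SD | 63% | 54% |
| Upper bound for the weaker contrast, f = 0.30 | 0.624 SD | 54% | 45% |
| Evenly spaced means, f = 0.33: vs lean | 0.844 SD | 83% | 76% |
| Evenly spaced means, f = 0.33: vs healthy obese | 0.422 SD | 24% | 18% |

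The evenly spaced pattern (lean, healthy obese, insulin resistant) is an illustration; the plan states none.

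**The case against.** The strongest reply is that the plan says only Cohen's f, without a convention, and that an unweighted f can equal 0.33. That is true, and it is why the fix allows the convention to be stated instead. It does not make the figure reproducible: it needs one particular pattern of means that the plan does not give, and under that pattern one aim contrast has almost no power.

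Second, the discrepancy is harmless. On the size-weighted definition the study detects a slightly smaller effect than claimed, and the label of medium is not affected by the move from 0.33 to 0.30. This stands, and it limits the weight of the arithmetic point.

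Third, the plan powers the omnibus test, treats Tukey-Kramer as a post-hoc step, and sets no go/no-go rule on pairwise significance; estimates and variances can also inform a later study. This stands too, so the pairwise figures are a request for fuller reporting. The request is reasonable because the aims are worded as those contrasts.

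Finally, the plan also mentions a generalized linear model with covariates. The pairwise figures here are for unadjusted comparisons and do not describe that analysis.

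**Conclusion.** The concern holds. From its stated inputs the minimum detectable f is 0.30, not 0.33, and 0.33 corresponds to 87% power instead of 80%. The error is conservative for the overall F test and gives no reason to change the sample size.

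The more useful point for readers is the missing sensitivity. Each contrast named in Aims 1 and 2 needs a difference of 0.82 SD (three-group family) or 0.875 SD (four-group family) for 80% power, and at the stated f the weaker contrast cannot exceed 63% or 54%.

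These results assume normal outcomes with equal variance, the full 70, 20 and 20 children analysed, and no covariate adjustment. The 0.30 also assumes f weighted by group size.

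**What to change.** In the Sample Size Justification:

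- Restate the result as: omnibus F test, N = 110, three groups, f weighted by group size, minimum detectable f = 0.30. Alternatively, keep 0.33 and state the convention and pattern of means that give it.
- Add the differences detectable with 80% Tukey-Kramer power and name the family: 0.82 SD (three groups) or 0.875 SD (four groups) for insulin resistant vs each comparator, and 1.02 or 1.09 SD for healthy obese vs lean.
- Say that the medium label applies to the omnibus f only.

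Naming the family also means reconciling the three groups used for power with the four listed for the ANOVA.

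The cost is one corrected figure and one or two sentences, with no change in enrolment. The omnibus figure improves slightly, while the stated pairwise sensitivity will look less favourable than the present text suggests.
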